6.6 Adverse Events Assessments

6.6.1 *Definition*

An AE is defined as any untoward medical occurrence in a subject regardless of its causal relationship to study treatment. An AE can therefore be any unfavorable and unintended sign (including an abnormal laboratory finding or symptom) or disease temporally associated with the use of a medicinal product whether or not considered related to the medicinal product.

6.6.2 *Performing Adverse Events Assessments*

The investigator or designee will monitor each subject for clinical and laboratory evidence of AEs on a routine basis throughout the study. The investigator or designee will assess and record any AE in detail in the source document and on the appropriate eCRF including the date of onset, description, severity, duration, relationship of the AE to study drug(s), action(s) taken and outcome. AEs, whether in response to a query, observed by site personnel, or reported spontaneously by the subject will be reported on the appropriate eCRF.

6.6.3 *AE Collection Period*

All AEs that occur after the ICF has been signed must be reported in detail in the AE section of the eCRFs, documented in the source document and followed to a satisfactory resolution, until the investigator deems the event to be chronic or the subject to be stable, or until the subject's participation in the study ends.

Information to be collected includes type of event, date of onset, date of resolution, investigator-specified assessment of severity and relationship to study drugs, seriousness, as well as any required treatment or evaluations and outcome.

AEs resulting from concurrent illnesses, reactions to concurrent illnesses, reactions to concurrent medications, or progression of disease states must be documented as AEs. Pre-existing conditions (present before the start of the AE collection period) are considered concurrent medical conditions and should NOT be recorded as AEs, but must be documented in the Medical History section of the eCRF and in the source document. However, if the subject experiences a clinically significant worsening or complication of such a concurrent condition, the worsening or complication should be recorded as an AE. Investigators should ensure that the AE term recorded captures the change in the condition.

Each AE should be recorded to represent a single diagnosis. Accompanying signs (including abnormal laboratory values or ECG findings) or symptoms should NOT be recorded as additional AEs. If a diagnosis is unknown, sign(s) or symptom(s) should be recorded as an AE(s). Changes in laboratory values or ECG parameters are only considered to be AEs if they are judged to be clinically significant (ie, if some action or intervention is required or if the

investigator judges the change to be beyond the range of normal physiological fluctuation). If abnormal laboratory values or ECG findings are the result of pathology for which there is an overall diagnosis (eg, increased liver enzymes in hepatitis), the diagnosis only should be reported as an AE.

Pre-planned procedures (surgeries or therapies) that were scheduled prior to the start of AE collection are not considered AEs. However, if a pre-planned procedure is performed early (eg, as an emergency) due to a worsening of the preexisting condition, the worsening of the condition should be captured as an AE. Elective procedures performed where there is no change in the subject's medical condition should not be recorded as AEs, but should be documented in the subject's source document and captured in the eCRF as procedures.

Any report of pregnancy identified for any female subject or for a female partner of a male subject should be reported immediately (within 24 hours of being informed) to the medical monitor. Pregnancies will be considered 'events of special interest' and will not be captured as serious adverse events (SAEs). The Pregnancy Reporting form will be utilized to obtain baseline and FU information. Pregnancies will be followed to termination or six weeks post-delivery for determination of resolution to the event. Subjects who become pregnant during treatment must immediately be withdrawn from the study.

The Medical Dictionary for Regulatory Activities (MedDRA), Version 20.0 or later, will be used to code all AEs.

6.6.4 Severity

The intensity of the AE will be rated by the investigator as mild, moderate or severe using the following criteria:

- Mild: Symptoms causing no or minimal interference with usual social and functional activities
- Moderate: Symptoms causing greater than minimal interference with usual social and functional activities
- Severe: Symptoms causing inability to perform usual social and functional activities

It should be noted that the clinical severity and seriousness of an AE are not synonymous, eg, a severe headache is not classified as serious until it meets the required elements as an SAE.

The maximum severity attained for each AE reported will be recorded in the eCRFs.

6.6.5 Relationship

The investigator's assessment of an AE's relationship to study drug is not a factor in determining whether the AE is reported in the AE section of the eCRF. If there is any doubt as to whether a clinical observation is an AE, the event should be reported.

The relationship or association of the study drugs in causing or contributing to the AE will be characterized by the investigator using the following classifications and criteria:

Definite – The AE:

- Follows a reasonable temporal sequence from drug administration;

- Abates upon discontinuation of the drug (dechallenge); and/or
- Is confirmed by reappearance of the reaction on repeat exposure (rechallenge).

Probable – The AE:

- Follows a reasonable temporal sequence from drug administration;
- Abates upon discontinuation of the drug; and/or
- Cannot be reasonably explained by the known characteristics of the subject's clinical state.

Possible – The AE:

- Follows a reasonable temporal sequence from drug administration;
- Could have been produced by the subject's clinical state or by other modes of therapy administered to the subject.

Unrelated – The AE:

- Is definitely produced by the subject's clinical state or by other modes of therapy administered to the subject.

6.6.6 *Expectedness*

AEs must be assessed as to whether they were expected to occur or unexpected, meaning not anticipated based on current knowledge about the investigational compound found in the protocol, Investigator Brochure (IB), product insert, or label. Categories are:

- Unexpected - nature or severity of the event is not consistent with information about the condition under study or intervention in the protocol, consent form, product brochure, or IB.
- Expected - event is known to be associated with the intervention or condition under study.

6.6.7 *Clinical Significance*

Changes in laboratory values, ECG parameters or other diagnostic procedures are only considered to be AEs if they are judged to be clinically significant (ie, if some intervention or therapy is required or if the investigator judges the change to be beyond the expected variation). Any changes or abnormalities will be assessed by the investigator, indicating whether the value is clinically significant or not clinically significant directly on the laboratory report or ECG tracing.

6.6.8 *Serious Adverse Events*

6.6.8.1 *Definition*

An SAE is defined by the investigator or sponsor as any AE occurring during an investigational study that results in any of the following outcomes:

- Death
- Life-threatening AE

- Hospitalization or prolongation of existing hospitalization
- A persistent or significant disability (substantial disruption of the ability to conduct normal life functions)/incapacity
- A congenital anomaly/birth defect
- Important medical event requiring medical or surgical intervention

The report of an SAE may require information about the study procedures or about the study drug that will result in the need to unblind the treatment. Codes linking randomization number for each subject to actual treatment will be secured in a sealed, opaque envelope and maintained in a locked drawer in the research center and/or the research pharmacy.

Research subjects will be instructed to notify the research center for any emergent condition and will be given the emergency contact number for the study during the consenting process.

Important medical events that may not be life threatening, result in death, or require hospitalization may be considered an SAE when, based upon appropriate medical judgment, they may jeopardize the subject and may require medical or surgical intervention to prevent one of the outcomes listed in this definition. Examples of such medical events include allergic bronchospasm requiring intensive treatment in an emergency room or at home, blood dyscrasias or convulsions that do not result in subject hospitalization, or the development of drug dependency or drug abuse. Hospitalizations to conduct diagnostic procedures will be captured in the eCRF on the PROCEDURES AND DIAGNOSTICS page.

6.6.8.2 *Reporting Serious Adverse Events*

Any AE considered serious (see Section 6.6.8 Serious Adverse Events) by the investigator that meets the previously mentioned criteria must be reported to the following numbers within 24 hours from the time when site personnel first learn about the event.

SAE Fax line: [REDACTED]

SAE email: [REDACTED]

A written report will follow as soon as possible and should consist of the SAE report and other documents, including the following pages from the eCRF: the demographics page(s), the medical history page(s), the AE page(s), and the concomitant medications page(s). If the subject is hospitalized because of or during the course of an SAE, then the investigator should attempt to obtain a copy of the hospital discharge summary and any pertinent laboratory or diagnostic reports, and provide them to the sponsor or designee as soon as possible.

For any information not available at the time of the first report that becomes available later, the investigator should add this information to the initial SAE section of the eCRFs and provide any additional written documentation to the above number immediately or within 24 hours of receipt.

The sponsor or designee will notify the appropriate regulatory agencies of any serious and unexpected SAEs associated with the use of the study drugs according to regulations. Copies of any reports to regulatory agencies regarding serious and unexpected suspected adverse reactions (SUSAR) will be provided to the investigators by the sponsor or designee for review and submission to the IRB. A report received for a serious, unexpected, suspected adverse reactions (SUSAR) will be unblinded for regulatory reporting.

The investigator is responsible for informing his or her IRB of any SAEs at that site. Copies of SAE correspondence with the IRB, ethics committees, regulatory authorities, and other physicians must be submitted to the sponsor's Clinical Services Department.

A subject experiencing one or more SAEs will receive treatment and FU evaluations by the investigator, or they will be referred to another appropriate physician for treatment and FU. Withdrawal from the study and all therapeutic measures will be at the discretion of the investigator at the site.

All SAEs will be followed until resolution or should the event become indistinguishable from the chronic disease condition, the subject will be followed for a minimum of 30 days after study drug administration and subsequently all events will be closed. Pregnancies will be followed until six weeks following delivery to determine the outcome.

6.6.9 Treatment-Emergent Adverse Events

A TEAE is defined as any adverse event with onset or worsening reported by a subject from the time that the first dose of study drug is taken until 30 days following discontinuation of study drug administration.

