Another study conducted in adults with SHPT, stage 3 or stage 4 CKD and VDI provided multiple-dose data on serum 25-hydroxyvitamin D₃, total 25-hydroxyvitamin D and total 1,25-dihydroxyvitamin D for population PK analysis [Sprague 2014]. In this study, subjects received daily bedtime doses of 30, 60 or 90 µg of CTAP101 or placebo for six weeks and were monitored for six weeks after the last dose. Mean serum 25-hydroxyvitamin D₃ increased gradually in a dose-proportional manner. The t_{max} after the last dose was 38–43 hours with a tendency toward higher values with increasing dose. Mean C_{max} , after adjustment for baseline values, was 28, 60 and 86 ng/mL for the 30, 60 and 90 µg groups, respectively. Calcifediol exposures, calculated as mean background-adjusted AUC, were dose proportional and the mean $t_{1/2}$ was between 25 and 50 days. Steady-state serum 25-hydroxyvitamin D₃ levels were not reached after six weeks of dosing.

The effect of alcohol on the release of calcifediol from CTAP101 Capsules was evaluated in an in vitro dissolution study. Concentrations of ethanol up to 40% by volume had no effect on the release of calcifediol.

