An Interactive Response System (IRS) will provide study treatment group assignments (using a computer-generated randomization code provided by the IRS vendor) and dosing adjustments. An independent, unblinded Data Safety Monitoring Board (DSMB) will oversee the IRS and verify the appropriateness of all dosing adjustments, and monitor subject safety and the effectiveness of CTAP101 Capsules at regular intervals. Members of the DSMB will also conduct periodic reviews of study conduct to verify that all required data are captured to a sufficiently high degree (>95%) and within specified time frames (usually within 5 days), and to promptly recommend appropriate corrective actions to address any noted deficiencies, in an effort to minimize missing data. Specific responsibilities and activities of the DSMB will be defined in the charter ratified at the pre-study organizational meeting. These responsibilities will include the completion of an interim analysis of the data obtained in Cohort 1 to justify a starting dose for Cohort 2, and an interim analysis of the data obtained from Cohort 2 to justify a starting dose for a separate phase 2 study in subjects having ages of 1 month to <8 years.

Subjects receiving treatment prior to study enrollment with calcitriol or another 1 α -hydroxylated vitamin D analog, or calcimimetics prior to study enrollment will forgo further dosing with these agents for the duration of the study and complete an 8-week washout period prior to baseline assessments. Subjects receiving vitamin D supplementation at a rate above 1,700 IU/day or 50,000 IU (1,250 mcg) per month prior to study enrollment must reduce the dose to ≤1,700 IU/day for the duration of the study and undergo an 8-week washout period prior to baseline assessments if serum total 25-hydroxyvitamin D is ≥30 ng/mL. The washout period is unnecessary if serum total 25-hydroxyvitamin D is <30 ng/mL. Subjects will complete a 6-week follow-up (FU) period after completing the 26-week treatment period or after early termination (ET).

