3.2 Rationale for Study Design and Control Group

EirGen is developing CTAP101 Capsules for the treatment of SHPT in pediatric patients with stages 3 or 4 CKD and VDI. The active ingredient in CTAP101 Capsules is calcifediol, which is formulated as ER capsules for oral administration.

The present study is designed to compare the efficacy of CTAP101 Capsules to matching placebo with regard to reducing mean plasma iPTH levels by at least 30% from pre-treatment baseline in pediatric patients with stage 3 or 4 CKD and VDI. The study will also examine the safety and tolerability of CTAP101 Capsules compared to placebo. This adequate and well-controlled, randomized and double-blind study provides the best means to evaluate efficacy, safety and tolerability of CTAP101 Capsules because no therapy has yet been approved by the FDA to treat elevated iPTH levels associated with low serum total 25-hydroxyvitamin D levels in pediatric CKD patients. In other studies conducted in adult subjects with stage 3 or 4 CKD and SHPT, administration of placebo therapy for 26-weeks has not been shown to result in untoward effects [Coyne 2006; Coburn 2004]. However, since iPTH values >900 pg/mL have been associated with increased risk of fracture in hemodialysis patients [Jadoul 2006], subjects will be terminated from this study for confirmed iPTH levels >900 pg/mL.

The starting dose of 30 mcg per day is based on the results from two phase 3 studies (CTAP101-CL-3001 and CTAP101-CL-3002) conducted in adults with SHPT, stage 3 or 4 CKD and VDI. Data from these studies demonstrated that steady-state serum 25-hydroxyvitamin D₃ levels were reached after 12 weeks of treatment at daily doses of 30 or 60 mcg of CTAP101 Capsules. Accordingly, upward dose titration is not allowed in the present study until after 12 weeks, when subjects receiving the initial dose of CTAP101 Capsules have attained steady-state blood levels of serum total 25-hydroxyvitamin D. A 26-week treatment period was selected for this study to ensure that steady-state will be attained in subjects who undergo upward dose titration at the beginning of treatment week 13.

Previous PK analyses in adult CKD patients have determined that the $t_{1/2}$ of serum 25-hydroxyvitamin D₃ is approximately 30 days (CTAP101-CL-2008). Consequently, the post-dosing FU period of 6-weeks should be sufficient for determining the $t_{1/2}$ in pediatric patients.

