5.5 Overdose and Toxicity

CTAP101 Capsules contain calcifediol, which is a vitamin D metabolite. An increased serum calcium has been shown to be one of the first indicators of toxicity associated with vitamin D overdose and is frequently used as a surrogate marker of toxicity in patients treated with vitamin D therapy. Progressive hypercalcemia may require emergency attention. Acute hypercalcemia may exacerbate tendencies for cardiac arrhythmia and seizure, and may potentiate the action of digitalis. Chronic or repeated hypercalcemia can lead to generalized vascular and soft tissue calcification.

No specific antidote to CTAP101 Capsules exists. If overdose is suspected, the subject should be monitored closely and kept under observation by a physician. The $t_{1/2}$ of calcifediol is approximately 30 days in adult patients with stage 3 or 4 CKD. Possible clinical and laboratory events include hypercalcemia and hypercalciuria.

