7.2 Treatment Period (Weeks 1-26)

7.2.1 Visits 4-10 (Days 8-71)

- May occur ± 3 days of scheduled day
- AE assessment
- Concomitant medications

- VS measurements
- Blood samples drawn for:
 - Chemistry (partial panel)
 - Plasma iPTH
 - Serum total 25-hydroxyvitamin D

7.2.2 *Visits 11-12 (Days 83-84)*

- Must occur on the scheduled days
- AE Assessment
- Concomitant medications
- VS measurements
- Blood samples drawn for all subjects at 0 (pre-dose), 6 and 12 hours and additionally, only for subjects assigned to intensive PK evaluation, at -2, 2, 4 and 8 hours after dosing on Day 83 for:
 - Chemistry (partial panel)
 - Serum 25-hydroxyvitamin D₃, [REDACTED]
- Blood samples drawn at 24 hours ±4 hours before dosing on Day 84 for:
 - Chemistry (partial panel)
 - Serum 25-hydroxyvitamin D₃, [REDACTED]

7.2.3 *Visit 13 (Day 85):*

- Must occur on the scheduled day
- Urine pregnancy (for females of childbearing potential)
- AE assessment
- Concomitant medications
- Urine pregnancy (only for females of childbearing potential)
- VS measurement
- Urine chemistry and urinalysis
- Blood samples drawn at 48 hours ±4 hours before dosing for:
 - Chemistry (full panel) and hematology
 - Plasma iPTH
 - Serum total 25-hydroxyvitamin D
 - Serum 25-hydroxyvitamin D₃, [REDACTED]
 - [REDACTED]
- Drug accountability
- Patient reported palatability and acceptability

- Dispense assigned bottles of study drug

7.2.4 *Visits 14-21 (Days 92-169)*

- May occur ± 3 days of scheduled day
- Visits 14 and 16 are required only for subjects who underwent upward dose titration at visit 13
- AE assessment
- Concomitant medications
- VS measurements
- Blood samples drawn for:
 - Chemistry (partial panel)
 - Plasma iPTH
 - Serum total 25-hydroxyvitamin D

7.2.5 *Visit 22 (Day 183):*

- Must occur on the scheduled day
- Urine pregnancy (only for females of childbearing potential)
- AE assessment
- Concomitant medications
- VS measurements
- Urine chemistry and urinalysis
- Blood samples drawn for:
 - Chemistry (full panel) and hematology
 - Plasma iPTH
 - Serum total 25-hydroxyvitamin D
 - Serum 25-hydroxyvitamin D₃, [REDACTED]
 - [REDACTED]
- Patient reported palatability and acceptability
- Drug accountability

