7.3 Follow-up Period or Second PK Assessment

7.3.1 *Visit 23 (Day 190)*

- Must occur on the scheduled day
- Required only for subjects participating in the second PK assessment
- AE Assessment

- Concomitant medications
- VS measurements
- Blood samples drawn for:
 - Chemistry (partial panel)
 - Serum 25-hydroxyvitamin D₃, [REDACTED]

7.3.2 *Visit 24 (Day 197)*

- May occur ± 3 day of scheduled day
- Required only for subjects participating in the second PK assessment
- Concomitant medications
- AE assessment
- VS measurements
- Blood samples drawn for:
 - Chemistry (full panel) and hematology
 - Plasma iPTH
 - Serum total 25-hydroxyvitamin D
 - Serum 25-hydroxyvitamin D₃, [REDACTED]

7.3.3 *Visits 25-27 (Days 204-218)*

- Must occur on the scheduled days
- Required only for subjects participating in the second PK assessment
- AE Assessment
- Concomitant medications
- VS measurements
- Blood samples drawn for:
 - Chemistry (partial panel)
 - Serum 25-hydroxyvitamin D₃, [REDACTED]

7.3.4 *Visit 28/ET (Day 225)*

- May occur ± 3 day of scheduled day
- Concomitant medications
- AE assessment
- PE (including weight, height and BMI)
- VS measurements
- 12-lead ECG

- Urine chemistry and urinalysis
- Urine pregnancy (only for females of childbearing potential)
- Blood samples drawn for:
 - Chemistry (full panel) and hematology
 - Plasma iPTH
 - Serum total 25-hydroxyvitamin D
 - Serum 25-hydroxyvitamin D₃, [REDACTED]
 - [REDACTED]

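### The treatment-emergent window closes 30 days after the last dose, so adverse events first dated in about the last 12 days of follow-up, including at Visit 28, miss the AE incidence tables

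*Combined protocol and SAP*

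**What the plan says.** - **Window.** Section 6.6.9 defines a TEAE as an event with onset or worsening from the first dose "until 30 days following discontinuation of study drug administration".
- **Collection.** Section 6.6.3 requires every AE after consent to be recorded. Section 3.1 gives every subject six weeks of follow-up after week 26 or early termination. Section 7.3.4 schedules an AE assessment at Visit 28/ET on Day 225, with the allowance "May occur ± 3 day of scheduled day".
- **Tabulation.** The incidence summaries in Section 9.11.1.1 (all, drug-related, serious, leading to discontinuation, by severity, by system organ class and preferred term) are built on TEAEs. All AEs go into listings, and deaths have their own listing.
- **Half-life.** Section 5.5 says that the half-life "of calcifediol is approximately 30 days in adult patients with stage 3 or 4 CKD". Section 3.2 uses the same figure to justify the six-week follow-up. Section 1.12 reports from a repeat-dose study in adults with CKD that the mean half-life "was between 25 and 50 days".
- **Follow-up visits.** Under Sections 7.3.1 to 7.3.3, Visits 23 to 27 are held only for the second PK subset, which Section 5.6 draws from the active group. All other subjects have Visit 28 alone.
- **Examinations.** Table 1 and Appendix 1 place the only post-baseline physical examination and ECG at Visit 28/ET. Section 9.11.1.5 also mentions an ECG at Visit 22, which neither of them schedules.

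**The concern.** The plan collects AEs for six weeks after dosing but summarizes only about the first 30 days, and gives no reason for the difference. The drug is cleared slowly, so exposure is still material when the window shuts.

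The excluded stretch also contains the one follow-up visit that every completer has. Physical examinations and ECGs are primary safety endpoints (Section 9.8.2). A new finding at Visit 28 that is judged to be an AE, and dated to that visit, cannot be a TEAE in a completer. It would be recorded with severity, seriousness and relatedness, but would not enter the by-arm incidence tables where those attributes are summarized.

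The visits that fall inside the window are held only in part of the active arm, so the opportunity to find an AE at a scheduled visit within 30 days is uneven between arms.

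**Working it through.** **1. Length of follow-up.** Visit 22 is Day 183 (Section 7.2.5) and Visit 28 is Day 225 (Section 7.3.4). 225 − 183 = 42 days = 6 weeks, which reproduces the plan's stated follow-up.

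**2. Days outside the window.** Taking Day 183 as the end of dosing, 42 − 30 = 12 days, or 12/42 = 29% of follow-up. With ±3 days on Visit 28, the range is 39 − 30 = 9 to 45 − 30 = 15 days. If the last bedtime dose were on Day 182, the central figure would be 225 − 182 − 30 = 13. In each case Visit 28 lies outside the window.

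**3. Drug remaining.** Assuming first-order elimination, the fraction left t days after the last dose is 0.5^(t/h), where h is the half-life. It refers to drug-derived concentration above the endogenous baseline.

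| Half-life h | Day 30 | Day 42 |
|---|---|---|
| 25 days | 0.5^(30/25) = 44% | 0.5^(42/25) = 31% |
| 30 days | 0.5^(30/30) = 50% | 0.5^(42/30) = 38% |
| 50 days | 0.5^(30/50) = 66% | 0.5^(42/50) = 56% |

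The half-life of about 11 days in Section 1.12 would leave 15% at day 30, but it comes from healthy adults, not from patients with CKD.

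**4. Which visits fall where.** Days 190, 197, 204, 211, 218 and 225 are 7, 14, 21, 28, 35 and 42 days after Day 183. Visits 23 to 26 are inside the window; Visits 27 and 28 are outside it.

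**5. Who has visits inside the window.** Section 5.6 plans 20 second-PK subjects per cohort, all active. Of 72 active subjects:
- As planned: 20 + 20 = 40 (56%) have Visits 23 to 27, and 32 (44%) have only Visit 28.
- Cohort 2 has 36 × 2/3 = 24 active subjects. The second subset must be other than the 10 in intensive PK, so at most 24 − 10 = 14 are available. The total is then 20 + 14 = 34 (47%), and 38 (53%) have only Visit 28.

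All 36 placebo subjects have only Visit 28. Across the trial that is 36 + 32 = 68 to 36 + 38 = 74 of 108 subjects. No placebo subject has a scheduled follow-up visit inside the 30 days.

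**The case against.** The strongest reply is that little is lost, and several stronger readings that a reader might infer do fail.

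- **That late events drop out of the safety tables altogether.** They do not. Laboratory and ECG shift tables run to Visit 28/ET (Sections 9.11.1.2 and 9.11.1.5), and all AEs are listed. Only the TEAE incidence tables are cut.
- **That high calcium or phosphorus first seen on Day 225 would disappear.** Such values enter the laboratory tables. The hypercalcemia and hyperphosphatemia proportions in Section 9.11.2 carry no 30-day limit. A single new Day 225 value would miss them because they require two consecutive visits, not because of the TEAE window.
- **That most subjects with drug on board have only Visit 28.** Most is right for the whole trial, but in the active arm it is only about half.
- **That everything reported at Visit 28 is lost.** TEAE status follows onset or worsening, not detection. An AE reported at Visit 28 that began by day 30 counts, and AEs with a missing onset date default to treatment-emergent (Section 9.11.1.1).
- **That the comparison between arms is shown to be biased.** The same window applies to both arms. The documents show unequal visit-based detection, not a resulting bias of known size.

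It is also fair to say that 31% to 56% of the drug would remain at day 42, so residual exposure alone does not single out day 42 as the end point. The 30-day figure matches the minimum SAE follow-up in Section 6.6.8.2. First onset this late off drug should be uncommon. Section 9 defers some detail to a Statistical Analysis Plan, so a table of post-treatment AEs may be planned where it cannot be seen here.

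What stands after all this is the mismatch between AE collection and AE tabulation, and the position of Visit 28 outside the window.

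**Conclusion.** The point holds as a minor, inexpensive improvement. AEs with onset, or first dated, in about the last 12 days of follow-up (9 to 15 with the visit window) are recorded but are left out of the AE incidence tables, at a time when about half the drug remains at the start of that stretch. For completers this includes any AE first identified and dated at Visit 28.

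The conclusion rests on three assumptions: dosing ends at about Day 183, elimination is first-order, and adult CKD half-lives apply to children, for whom the documents give no value. The mismatch in days does not depend on the half-life; only the statement about remaining drug does. The number of events affected cannot be derived from the documents and is expected to be small.

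**What to change.** In Section 6.6.9, define TEAEs as events with onset or worsening from the first dose through Visit 28/ET, meaning the end of the six-week follow-up. In the Section 9.11.1.1 tables, show onset on treatment and onset during follow-up separately. Keep the 30-day version as a supplementary table for comparison with other work that uses that cut.

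This brings in the one follow-up visit scheduled for every subject. It lessens the uneven visit-based detection between arms but does not remove it, since Visits 23 to 27 remain confined to part of the active arm.

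The cost is one changed definition and its programming, with no new visits, samples or data. The downside is that a few more unrelated late events will be counted in both arms; the separate follow-up column keeps them visible as such.
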